### 11.2 Eliciting Adverse Events

All trial subjects will have an enquiry about co-morbidities, medications and new or unexpected symptoms at each follow-up visit, as well as diabetes assessment.

### 11.3 Principal Investigator/Trial Centre Responsibilities

The PI will be required to report all AEs/SAEs which occur during the Trial on an Adverse Event Form and keep a record in the case report form (CRF). AEs will be collected from the time the participant receives their first dose of IMP until one month after the last trial visit (visit 6, week 20). The AEs will be reported at agreed intervals to the DSMB and if there is any concern a DSMB meeting will be convened.

#### 11.4 Assessing AEs

The PI should assess the AE for seriousness and causality. The PI should exercise medical judgement in deciding whether an Adverse Event/Reaction is serious in other situations. All SAEs should be reported to STU by the PI immediately (within 24hrs) of becoming aware of the event. The PI will be asked to grade all AEs in relationship to the study treatment according to their clinical judgement as follows:

##### **Causality:**

- **Not related** – temporal relationship of the onset of the event, relative to administration of the product, is not reasonable or another cause can by itself explain the occurrence of the event.
- **Unlikely to be related** – temporal relationship of the onset of the event, relative to administration of the product, is likely to have another cause which can by itself explain the occurrence of the event.
- **Possibly related** – temporal relationship of the onset of the event, relative to administration of the product, is reasonable but the event could have been due to another, equally likely cause.
- **Probably related** – temporal relationship of the onset of the event, relative to administration of the product, is reasonable and the event is more likely explained by the product than any other cause.
- **Very likely** – temporal relationship of the onset of the event, relative to administration of the product, is reasonable and there is no other cause to explain the event, or a re-challenge is positive.

#### 11.5 Reporting procedures

All SAEs must be reported immediately (within 24 hrs of being made aware of the event) by the PI to STU within 24 hours of receipt.

Initial reports should be submitted as soon as the following minimum criteria are met:

- A suspected SAE is identified;
- An identifiable participant (e.g. trial participant code number);
- An AE assessed as serious and unexpected, and for which there is a reasonable suspected causal relationship;
- An identifiable reporting source (e.g. clinical research fellow).

Following the Initial Report, all SAEs should be followed to resolution. Following the initial report the PI may be requested to provide further information. The participant should only be identified by trial number, date of birth and initials. The participant's name should not be used on any correspondence. The PI is also responsible for reporting AEs to their NHS Trust as per their local NHS Trust procedures.

### **11.6 Sponsor and Chief Investigator Responsibilities**

The Sponsor (or delegate – STU) is responsible for ensuring all SAEs, SARs and SUSARs (except those specified in this protocol as not requiring reporting) will be reported in the appropriate timescale to the MHRA, REC, MPA and the Regional Ethical Review Board (RERB) in Linköping.

STU is responsible for ensuring all SUSARs from Cardiff and Linköping (except those specified in this protocol as not requiring reporting) will be reported in the appropriate timescale to the MHRA, REC, MPA and RERB.

Once an SAE is received by STU, the SAE will be sent to the CI (or appropriate delegate) for clinical review (assessment of causality and expectedness). Fatal and life threatening SAEs should be assessed by the CI within 24 hours of receipt. Non-fatal or non-life-threatening SAEs should be assessed by the CI within 4 days of receipt.

Only SUSARs should be expedited to MHRA, MPA, RERB and REC. STU (UK) and Karolinska Trial Alliance (Sweden) will report according to the following timelines:

Fatal and life threatening SUSARs not later than 7 days after receipt; Non-fatal or non-life-threatening SUSARs not later than 15 days after receipt. Follow up information should be reported within 8 days of receipt of the follow up information. A copy of the SUSAR report should be provided to the Sponsor.

In addition to reporting to the relevant REC, RERB, MHRA and MPA, SUSARs will also be reported to all members of the TMG. The CI shall ensure that all co-investigators receive regular safety updates of SAE's and SUSARs that occur in relation to the IMP in the trial.

Dose interrupting and suspension of dosing will be managed as per the risk mitigation, see section 7.

#### ***The CI is responsible for assessing expectedness***

No events other than those listed in section 10.2 are expected.

### **11.7 Urgent Safety measures**

Urgent safety measures which are implemented immediately by the PI should be notified to the Trial Manager immediately, along with the reasons for the measure being taken.

The CI (or delegate – STU) shall be responsible for reporting urgent safety measures to MHRA, MPA, RERB and REC. This should include an initial contact with a medical assessor at the MHRA/MPA to discuss the urgent safety measure, followed by a detailed written report within 3 days. The report should include details of the urgent safety notification, the measures taken and the reason for the measures and details of any discussion with the MHRA and MPA medical assessor.

See section 8 for treatment stopping and withdrawal criteria.

### **11.8 Safety Report/ Line Listing**

One year following the granting of a CTA, and thereafter annually, the CI (or delegate – STU) should compile an annual safety report & DSUR for submission to the MHRA and REC, UK and the MPA and the Regional Ethical Review Board in Linköping.

## **12 ASSESSMENT OF EFFICACY**

Although not primarily a study designed to assess efficacy, laboratory and clinical measurements will be made that may indicate beneficial therapeutic trends associated with C19-A3 GNP administration. These have been specified as secondary endpoints.

### **12.1 Efficacy Parameters**

#### **12.1.1 Metabolic outcomes**

Residual insulin production will be assessed by measurement of stimulated C-peptide production during the MMTT using the area under the curve (AUC) approach. The normalized AUC will be calculated for each subject at 14 weeks and compared versus baseline (visit 1). Stimulated urine c-peptide creatinine ratio will also be measured as an alternative measurement.

Likewise, change in glycated haemoglobin (as measured by % HbA1c levels), daily insulin usage, and mean amplitude of glucose excursions will be measured/recorded as specified in the schedule of visits and compared with baseline.

For objective assessment of hypoglycaemia continuous glucose monitoring will be conducted for 3 days at baseline and prior to the final follow up visit. Hypoglycaemia frequency and standard deviation and interquartile range of glucose variability will be calculated from this data.

#### **12.1.2 Immunological outcomes**

Change in level or quality of T lymphocyte biomarkers of  $\beta$ -cell specific immune response will be assessed at 14 weeks (8 weeks for lymph nodes sampling) versus baseline, Levels of T lymphocyte biomarkers are measured as the numbers of cytokine-producing T cells responding to PPI C19-A3 or other  $\beta$ -cell autoantigenic peptides and the numbers of cytokine and other immune gene transcripts produced in response to stimulation with PPI C19-A3 or other  $\beta$ -cell autoantigenic peptides in vitro. A potentially important biomarker of therapeutic efficacy would be an increase in the number of responder T cells synthesizing the immune regulatory cytokine IL-10, or a decrease in the number of responder T cells synthesizing the pro-inflammatory cytokines IFN- $\gamma$ .

Changes in the quality of the immune response can also be measured by assays that specifically detect the ability of post-treatment CD4 T cells to regulate pre-treatment pro-inflammatory responses.

Changes in the level or quality of islet cell autoantibody biomarkers of  $\beta$ -cell specific immune response will be measured at 0, 14 weeks and compared with levels at baseline and between

groups. A potentially important biomarker would be a reduction in levels of islet cell autoantibodies. Changes in serum levels of cell free DNA derived from beta cells and T cells will be measured to provide potentially important biomarkers of beta cell and T cell death.

## **12.2 Procedures for Assessing Efficacy Parameters**

### **12.2.1 Insulin secretion**

C-peptide production in the MMTT assay will be assessed using the AUC approach. Levels of glucose, and C-peptide will be assessed from blood samples taken during the test. Stimulated C-peptide will be the area under the (C-peptide/time) curve from time 0 to 120 minutes, and this will be calculated by the trapezoidal rule. The AUC will be normalized for time interval by dividing it by the number of minutes over which AUC was determined; the number is expected to be 120 minutes but may differ in some cases. A urine sample after 120 minutes will be taken for urine C-peptide creatinine ratio which has been proposed as a surrogate marker of insulin secretion.

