**Figure 4 Sample management flowchart**

## 6.18 Laboratory procedures

### 6.18.1 Stimulated secretion of C-peptide

For screening, a post-meal random serum sample in the clinic or urine c-peptide/creatinine ratio will be measured. Patients are provided with a suitable container (boric acid preservative) and asked to void their bladder (and discard this urine) prior to their first meal of the day. They are then asked to substitute their first meal of the day with Ensure Plus and asked not to pass any urine until 2 hours after the Ensure Plus meal and take a sample of urine into the container at this time. These samples will be assayed in the laboratory in Diabetes Research Unit Cymru Laboratories in Swansea for urine c-peptide and creatinine.

During the study secretion of c-peptide will also be tested using the Mixed Meal Tolerance Test method (MMTT). Briefly, the test is performed in the morning (between 7 and 10 AM). The participant must be fasting and have had no food or drink (with the exception of water), and no smoking is permitted from 12 (midnight) or 8 hours prior to the start of the test. Tests should be conducted only if fasting value by capillary blood glucose meter is between 3.9-11.1mmol/L. Participants should withhold taking long acting insulin on the morning of the test. They can take very short acting insulin (e.g. Humalog, Apidra, or Novorapid) up to 2 hours before the test. They can take regular insulin up to 6 hours before the test. If the subject is using an insulin pump, they should be advised to continue their basal regime but not have a bolus.(80)

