The procedures are as follows. Start IV line. Obtain baseline blood samples at 0 minutes, and any other test samples required at that visit (e.g. HbA1c, T cell studies, PBMCs islet cell autoantibodies). For each time point blood samples are 1.2 ml fluoride tube for glucose and 1.2 ml serum tube for C-peptide. In addition, for each test the first sample (0 minutes) and the last sample (120 minute for MMTT) will be used to obtain a meter ketone reading, which is recorded. A first blood sample is drawn immediately before the participant starts drinking the liquid meal (formal "baseline samples"). The patient is given the standardized liquid meal: Ensure Plus 6 ml/kg (Maximum 360ml) to be ingested within 5 minutes. Blood samples are drawn at times: 15, 30, 60, 90 and 120 minutes, after the end of ingestion of Ensure Plus (note: time runs from the start of ingestion). After the test is completed, the participant eats and receives insulin as appropriate and prescribed by the local investigator. A urine sample at the 120 minute time point will also be collected for c-peptide creatinine ratio as an alternative marker of insulin production.

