5.1.2. Secondary outcomes

Differences in the parameters set below will be calculated for each patient and summarised by mean and standard deviations. Potential differences between patients receiving treatment within and outside treatment schedule will also be explored, if required.

- T cell responses to C19-A3 GNP as determined by changes from baseline of interferon gamma and IL-10 ELISPOT responses to this peptide in blood following treatment at weeks 0, 9 and 14.
- T cell responses to C19-A3 GNP as determined by changes from baseline of interferon gamma and IL-10 ELISPOT responses to this peptide in

draining axillary lymph node before treatment and following the last treatment administration (four aspirations: before and after visit 1 and visit 3)

- Changes in additional immunological biomarkers (e.g. flow cytometry profiles, T reg assays, autoantibodies, beta cell and T cell free DNA markers) from baseline at week 0, 9 and 14.
- Effects on residual insulin requirement and c-peptide secretion at week 14 as compared to baseline as assessed by secreted C peptide AUC after a mixed meal tolerance test and a stimulated urine c-peptide test.
- Effects on glycaemic control assessed by blood sugar profiles and HbA1c at week 14 as compared to baseline
- Scores on quality of life and diabetes self-management (week 0 and week 14).

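### The C-peptide AUC may be averaged over different windows at baseline and week 14, so an unchanged patient with a rising curve can show a false change

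*Protocol*

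**What the plan says.** Protocol 12.2.1 sets the measure: "Stimulated C-peptide will be the area under the (C-peptide/time) curve from time 0 to 120 minutes", by the trapezoidal rule. It then says "The AUC will be normalized for time interval by dividing it by the number of minutes over which AUC was determined", and adds that "the number is expected to be 120 minutes but may differ in some cases". It gives no minimum window, no requirement that a patient's two visits share a window, and no flag for a short one. Protocol 12.1.1 compares the normalised value at week 14 with visit 1 in each subject.

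SAP 5.1.2 takes the within-patient difference, "as assessed by secreted C peptide AUC after a mixed meal tolerance test", and summarises it by mean and standard deviation, with no algorithm of its own. SAP 5.2 offers worst-case, last-observation-carried-forward and mean-value imputation, with a complete-case analysis alongside. It does not say whether a missing data point can be one sample within a meal test or only a whole AUC.

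On timing, Protocol 6.18.1 says "Blood samples are drawn at times: 15, 30, 60, 90 and 120 minutes" and continues "after the end of ingestion of Ensure Plus (note: time runs from the start of ingestion". The drink is "to be ingested within 5 minutes", and the time-0 sample is taken just before drinking begins.

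**The concern.** Dividing by the minutes covered turns an AUC into a time-averaged concentration. Two such averages are comparable only if they cover the same part of the curve. C-peptide after a meal typically starts at its fasting level and rises, so an average over 0 to 90 minutes leaves out a later, often higher, stretch that the 0 to 120 average includes. Subtracting one from the other then mixes any true change with a difference in window.

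The two time origins in 6.18.1 raise a smaller version of the same problem. If a site counts from the end of drinking at one visit and from the start at the other, the samples fall at different points on the same curve.

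Protocol 3.4 requires residual C-peptide so that unexpectedly rapid loss can be detected, and 10.3 lists the meal-test AUC among the clinical monitors of disease exacerbation. With 8 patients and no control group, a false fall in one patient has no comparison group to be checked against.

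**Working it through.** The plan states no expected AUC, change or standard deviation for this endpoint, so there is no figure of its own to reproduce. The check applies the protocol's rule to curves that are identical at both visits, so the true change is zero.

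**Inputs from the documents:** samples at 0, 15, 30, 60, 90 and 120 minutes; trapezoidal AUC divided by minutes covered; drinking time up to 5 minutes; 8 patients.

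**Assumed:** five C-peptide curves, because the documents give none.

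**Formula.** Let M90 and M120 be the averages over 0–90 and 0–120 minutes, and L the average over the last 30 minutes. Then M120 = (90 × M90 + 30 × L)/120, so the false relative change when week 14 stops at 90 minutes is

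M90/M120 − 1 = 0.25 × (M90 − L)/M120.

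It is zero when L equals M90 and negative when the last half hour is higher. It would be positive if the curve fell far enough; none of the assumed curves does.

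**Worked example, still-rising curve** (100, 115, 140, 200, 260, 300 pmol/L):
- AUC 0–90 = 1612.5 + 1912.5 + 5100 + 6900 = 15525, so M90 = 15525/90 = 172.5.
- AUC 0–120 = 15525 + 8400 = 23925, so M120 = 23925/120 = 199.4.
- Week 14 short: 172.5/199.4 − 1 = −13.5%. Baseline short: 199.4/172.5 − 1 = +15.6%.

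| Assumed curve (pmol/L) | M120 | M90 | L | Week 14 ends at 90 min | Baseline ends at 90 min | 90-min value carried to 120 at week 14 |
|---|---|---|---|---|---|---|
| Flat, 200 | 200.0 | 200.0 | 200 | 0% | 0% | 0% |
| Peak at 60 min (200, 260, 340, 400, 370, 320) | 341.2 | 340.0 | 345 | −0.4% | +0.4% | +1.8% |
| Peak at 90 min (200, 240, 310, 430, 500, 480) | 393.1 | 360.8 | 490 | −8.2% | +8.9% | +0.6% |
| Linear, 200 to 400 | 300.0 | 275.0 | 375 | −8.3% | +9.1% | −2.1% |
| Still rising, 100 to 300 | 199.4 | 172.5 | 280 | −13.5% | +15.6% | −2.5% |

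**Two rules, one lost sample.** The last column reads SAP 5.2 as carrying the 90-minute value forward within the test. For the still-rising curve this gives (15525 + 30 × 260)/120 = 194.4, or −2.5%, against −13.5% under 12.2.1. Nothing says which is primary.

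**Clock.** If every post-meal sample at one visit is 5 minutes late and nominal times are used, the still-rising curve gives 24875/120 = 207.3, or +4.0%. Across the five curves the range is 0% to +4.0%. The sign reverses if the late visit is baseline. If both visits use the same clock, the difference cancels.

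**Group mean.** One patient in 8 at −13.5% moves the mean percentage change by 13.5/8 = 1.7 points.

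**After the fix.** The same window at both visits gives 0% from shortening for every curve. With actual times, and the AUC cut at 120 minutes by interpolation, a 5-minute shift leaves −0.6% to 0.0%. Removing the normalisation is not a remedy: a 0–90 AUC divided by a fixed 120 gives −25% to −35%.

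**The case against.** The plan has a fair defence. Time-averaging is sound in itself, and 12.2.1 expects 120 minutes. The allowance for other durations may mean only small departures such as 118 or 123 minutes, for which dividing by actual minutes is right. Nothing in the documents points to tests ending at 60 minutes. The SAP has a missing-data section, and carrying the 90-minute value forward would remove most of the artefact on the rising curves. The parenthetical note in 6.18.1 can be read as settling the clock. All of this limits the size of the problem. What stands is that 12.2.1 sets no bound on the difference in window, SAP 5.2 does not say that it reaches inside a meal test, and the sentence in 6.18.1 contradicts itself.

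Three stronger readings are tempting, and the documents do not support them:
- **The group result would be visibly distorted.** One affected patient moves the mean by under 2 points on these curves. SAP section 4 says the sample is not powered for before–after differences.
- **The main safety analysis depends on this AUC.** SAP 5.1.1 analyses exacerbation through autoantibodies and T-cell responses. Protocol 10.3 lists HbA1c, blood sugars and insulin use beside C-peptide.
- **The 120-minute urine sample is contaminated by overnight urine.** For screening, 6.18.1 says patients are "asked to void their bladder (and discard this urine) prior to their first meal of the day", and the meal-test instructions do not repeat this. Silence does not show that no void takes place. Table 1 schedules other urine samples at visits 1 and 5, though without an order relative to the meal. No size can be given.

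**Conclusion.** The concern holds in a limited form. As written, Protocol 12.2.1 permits different averaging windows at the two visits being compared. On the five assumed curves, a test ending at 90 minutes at one visit produces a false change of 0% to about −14% if it is the week-14 test, or 0% to about +16% if it is the baseline test. The larger values need a curve that is high or still rising late in the test. The silence of SAP 5.2 about samples within a meal test means the same lost sample could be handled in two ways with different results.

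The clock conflict is a genuine inconsistency but secondary: at most about 4% on these curves, and only when a patient's two visits follow different clocks.

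These sizes rest wholly on assumed profiles, and the documents do not say how often a test would be shortened. Since the endpoint is secondary and descriptive, no formal conclusion is at risk. The practical risk is that one patient's C-peptide change is misread.

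**What to change.** **Protocol 12.2.1 and SAP 5.1.2.** Compute each patient's change over the same window at both visits, namely the longest one available at both, using actual sample times. Flag any window under 120 minutes. State that this rule is primary for incomplete meal tests and that SAP 5.2 imputation serves as sensitivity analysis.

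**Protocol 6.18.1.** Keep a single time zero, the start of ingestion. It agrees with the existing note and with the baseline sample taken before the drink. At most, also make the screening and meal-test urine instructions consistent on voiding before the meal.

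**Cost.** A few sentences, with no extra visits or samples. When one test is short, part of the other visit's curve goes unused for that patient, and that patient's change then covers a shorter interval than the others'. That is why the flag is needed.

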### **12.2.2 Insulin usage**

Subjects will record the daily insulin usage in their capillary blood glucose testing meters supplied for the study. Insulin usage will be recorded daily from the screening stage through to the end of the study. In particular, insulin usage should be recorded accurately for at least 7 consecutive days during the 2 weeks prior to visits at 0, 4, 8 weeks. The mean daily insulin usage over the 7 consecutive days (IU units/kg body weight/day) will thus be calculated for each subject.

### **12.2.3 Blood glucose variability**

Mean amplitude of glucose excursion (MAGE) will be calculated at 0 and 14 weeks using records from 72 hour CGM recordings.

### **12.2.4 Immunological outcomes**

See sections 6.15 and 12.1.

## **13 STATISTICS**

The primary aim of this study is provide patient safety data.  
The study will be open label.

## **14 SAMPLE SIZE**

The single group study provides 8 patients on active treatment from whom it will be possible to collect safety data. This is considered optimal to achieve sufficient data to inform future study designs and on which to base future sample size calculations.

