### **5.2 Dosing regimen**

C19-A3 GNP will be administered intradermally via CE marked Nanopass 600nm microneedles. 3 doses will be given at 4 weekly intervals. The dose given will be equivalent to 10ug of C19-A3 peptide. Thus the cumulative dose will be 30ug.

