### **5.4 Subject compliance**

Patients will be allowed 28 days +/- 3 days between treatments, but every effort should be made to dose every 28 days. Where a visit is > 3 days late it should be documented as a protocol violation and scheduled as soon as possible, with subsequent dosing visits recommenced on a 28 day schedule after this. Where the interval between 2 doses is > 42 days, the dose will be considered to have been missed and the subsequent dose should be given. Subject attendance and compliance will be recorded. If a treatment is missed the subject will continue in follow-up but an additional subject will be recruited, so that a total of 8 subjects will receive all 3 doses.

Patients will be allowed to attend for follow up visit 4 (week 9 or one week post final injection) +/- 1 day of schedule, visit 5 (week 14), +/- 1 week of visit schedule and visit 6 (week 20) must be a minimum of 85 days post final dose/+2 weeks. There will also be an optional visit 7 (week 52) at a minimum of 311 days post final dose +/- 2 weeks. There will be an optional skin blister, an optional skin biopsy and an optional contact hypersensitivity testing performed anytime post-dose (referring to post final dose). Any visits outside of this guidance will be considered a protocol deviation.

**Figure 2** Chart indicating dosing schedule

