### 5.5 Dosing strategy:

This is an open label uncontrolled early phase safety study, so no blinding or randomisation will be performed. In keeping with standard phase 1 study designs, no placebo or control group is included as the primary aim is to establish whether there are any major unexpected safety issues in the use of this IMP for the first time in man.

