## **15 PLANNED ANALYSIS**

### **15.1 Final**

Data cleaning and preparation process will be carried out prior to analysis.

All patients enrolled will be followed up and included unless they withdrew from the study before the administration of the first dose. An intention to treat analysis will be carried out. Per protocol analyses may also be carried out alongside the intention to treat analysis if necessary. The analyses will mostly consist of tables of data such as mean values (or geometric means if the data is log normal) together with standard deviations and ranges. For data such as scores, medians, and ranges may be used instead, and binary outcome variables will use percentages. Comparisons against baseline will be made using Student's t-tests for paired and unpaired samples; Mann-Whitney U test; Wilcoxon matched pairs test; p values <0.05 will be considered significant.

Since the primary aim of the study is to provide patient safety data and guide the development of an antigen specific immunotherapy programme, it may be a requirement for strategic planning of subsequent stages of clinical study development, that early analysis of trial data is conducted.

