3.3. Analysis populations

- Intention to treat population
All patients enrolled in the study
- Per protocol population
Patients receiving all three injections

4. Statistical Principle

The sample has not been powered to detect significant differences before and after treatments. Data will be analysed by simple descriptive statistics.

All patients enrolled will be followed up and included unless they withdrew from the study before the administration of the first dose. An intention to treat analysis will be carried out. Per protocol analyses may also be carried out alongside the intention to treat analysis if necessary.

Adherence to the intervention will be assessed by missed dose (protocol violation) and delayed / missed followup visits (protocol deviation).

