5.1. Analysis of outcomes

5.1.1. Primary outcome

Assessment of the safety of C19-A3 GNP administration in terms of adverse events at the dose used is the primary outcome. This includes general safety concerns, induction of hypersensitivity and exacerbation of β -cell specific autoimmunity with accelerated β -cell loss. All enrolled patients will be included in the following analysis.

General Safety

To address general safety concerns at screening and 0, 4, 8 and 14 weeks a physical examination will be conducted. A review of AEs will be performed at all visits according to seriousness, causality and expectedness. Types of AEs, body systems involved and outcomes of the AE will be categorised and analysed by incidence per person dose used. All AEs will be collated

Hypersensitivity

Patients will be observed for local and systemic reactions post injection. Number of local reactions will be analysed by incidence per person dose used, size of the erythema note and time taken for erythema note size to be reduced to < 1 cm will be analysed by mean and standard deviation. Systemic reactions will be analysed by incidence per person dose used. Therapies used and outcome will be counted and reported.

Exacerbation of β -cell specific autoimmunity with accelerated β -cell loss

Differences between week 0 and 14 will be calculated for each patient and summarised by mean and standard deviations for the following parameters:

- Measurement of islet cell autoantibodies (against insulin, GAD-65, IA-2 and ZnT8)
- Measurement of pro-inflammatory β -cell specific T cell responses (analytes to be defined)

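### Protocol section 14 calls 8 patients sufficient without stating any precision, and SAP 5.1.1 reports reactions only per person-dose with no interval; per-patient counts with exact intervals are needed

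*Protocol*

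**What the plan says.** Protocol section 14 opens with "The single group study provides 8 patients on active treatment from whom it will be possible to collect safety data" and continues: "This is considered optimal to achieve sufficient data to inform future study designs and on which to base future sample size calculations". No event rate, standard deviation, power or precision target accompanies either sentence.

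SAP section 4 says that the sample was not powered for before-and-after differences, and then: "Data will be analysed by simple descriptive statistics". Under SAP 5.1.1, adverse events and local reactions are summarised as incidence per person-dose, and so are systemic reactions: "Systemic reactions will be analysed by incidence per person dose used". Changes in laboratory and metabolic measures (SAP 5.1.1 and 5.1.2) are given as mean and standard deviation.

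Protocol 15.1 adds ranges, percentages for binary outcomes, and tests against baseline under which "p values <0.05 will be considered significant". That threshold is not linked to the sample size. Neither document plans a confidence interval for a rate, a mean or a standard deviation, or says how zero events should be read.

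**The concern.** Hypersensitivity is part of the primary objective (Protocol 4.1, SAP 1.2). A patient who is susceptible at one dose is likely to be susceptible at the next, so the natural unit is the patient. A person-dose denominator turns 8 patients into 24 units and hides how events are spread. Three local reactions in one patient and one reaction in each of three patients both give 3/24 = 12.5%, but they are 1/8 = 12.5% and 3/8 = 37.5% of patients.

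The stopping rule adds to this. Under Protocol section 7 and SAP 2.2.2, dosing ends in a patient who has a systemic hypersensitivity event needing more than local therapy. Such a patient can contribute only one such event, and may contribute fewer than three doses.

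Section 14 meanwhile says that the data suffice for planning later trials, without saying how precise they will be. At stake is whether the report shows how little an event-free result would exclude, and how uncertain the variability estimates are.

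**Working it through.** **Inputs from the documents**
- Patients: 8 (Protocol section 14).
- Doses: "3 doses will be given at 4 weekly intervals" (Protocol 5.2), so 8 × 3 = 24 planned person-doses.
- Replacement: a subject who misses a dose is replaced, "so that a total of 8 subjects will receive all 3 doses" (Protocol 5.4). The number dosed may therefore exceed 8.

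**The plan's own figure.** N = 8 can be neither reproduced nor refuted, because no calculation or target is given.

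**Upper limit after zero events in n units**
- Formulas: one-sided 95% limit = 1 − 0.05^(1/n); two-sided exact (Clopper-Pearson) limit = 1 − 0.025^(1/n).
- Person-doses, n = 24: 1 − 0.05^(1/24) = 11.7%; 1 − 0.025^(1/24) = 14.2%.
- Patients, n = 8: 1 − 0.05^(1/8) = 31.2%; 1 − 0.025^(1/8) = 36.9%.
- Patients, n = 10, if two were replaced: 25.9% and 30.8%.

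**How the two limits relate.** If doses were fully independent, a per-dose risk of 11.7% over three doses would give a per-patient risk of 1 − (1 − 0.1173)^3 = 31.2%, the same as the direct per-patient limit. If a patient reacted either to every dose or to none, the per-dose risk would equal the per-patient risk, and its limit would also be 31.2%. So 31.2% describes the patient's risk over the course in both cases, while 11.7% holds only per dose and only under independence.

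**Effect of stopping.** Suppose one patient has a systemic reaction at the first dose and is stopped, and the other seven complete. The incidence per person-dose is 1/(1 + 7 × 3) = 1/22 = 4.5%. The proportion of patients is 1/8 = 12.5%, with exact 95% interval 0.3% to 52.7%.

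**Chance of seeing at least one affected patient in 8:** 1 − (1 − p)^8.
- p = 5%: 33.7%
- p = 10%: 57.0%, so it is missed entirely with probability 0.9^8 = 43.0%
- p = 20%: 83.2%

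To exclude a 10% rate at one-sided 95% would take 29 event-free patients: ln 0.05 / ln 0.9 = 28.4, rounded up.

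**Precision of a standard deviation from 8 patients.** Assuming normal data, 7 degrees of freedom:
- lower 95% multiplier √(7/16.01) = 0.66
- upper 95% multiplier √(7/1.690) = 2.04

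For a comparison of means the required sample size varies with the square of the standard deviation. The compatible range is therefore 0.44 to 4.14 times the size computed from the estimate.

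**The case against.** Eight patients is a conventional size for a first-in-man study, and safety action here does not wait for an incidence estimate. There is a sentinel patient, individual discontinuation, suspension of all dosing after any SUSAR, and reports to the DSMB after the sentinel and the fourth patient. SAP section 4 already says that the study is unpowered and descriptive, SAP 5.1.1 collates all adverse events, and Protocol 15.1 allows percentages for binary outcomes. All of this stands, and nothing in this point asks for more patients. But the disclaimer in SAP section 4 concerns before-and-after differences. It does not speak to the precision of a reaction rate or a standard deviation, and it does not qualify section 14. An exact interval is itself a descriptive statistic.

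A reader might infer more than the documents support:
- Protocol 5.5 says that "the primary aim is to establish whether there are any major unexpected safety issues". This can be taken as a claim that 8 patients can settle the matter. It is the statement of an aim, made while explaining why there is no control group, and no detectable rate is claimed.
- It is tempting to say that an event-free result will be over-interpreted, or that the next trial will be mis-sized. Those are forecasts about readers and future planners. Section 14 does not say that these 8 patients alone will size a later trial, and Protocol 3.2 describes two earlier studies of the peptide without nanoparticles.
- It is also tempting to require that later trials be planned on an upper confidence limit of the standard deviation. That would write a future trial's rule into this SAP. It would also rest on normality, where Protocol 15.1 itself anticipates log-normal data.

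**Conclusion.** The point holds as a reporting weakness, not as a design error. Section 14 asserts sufficiency with no precision behind it, and the planned reaction measure is the less informative of two that the same data can provide. With no events, the person-dose denominator suggests an upper limit of 11.7% (14.2% two-sided), while the per-patient limit is 31.2% (36.9%).

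The per-patient figures assume only that patients are independent and that exactly 8 are dosed; with 10 dosed the limits fall to 25.9% and 30.8%. The multipliers of 0.66 to 2.04 for the standard deviation assume normal data and would apply on the log scale to log-normal measures. No planned analysis is invalid, and no decision within the trial changes.

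**What to change.** - **SAP 5.1.1:** keep the person-dose incidence. Beside it, report the number and percent of patients who received at least one dose and had at least one adverse event, at least one local reaction and at least one systemic reaction. Give each an exact (Clopper-Pearson) 95% interval, with the actual number dosed as denominator (8, or more if subjects are replaced).
- **Protocol section 14:** replace the sufficiency statement with what the design delivers. Zero events in 8 patients excludes only per-patient rates above about 31% (one-sided 95%) or 37% (two-sided). Standard deviations from 8 patients have 95% limits of about 0.66 to 2.04 times the estimate if the data are normal, so they are preliminary inputs to later sample-size calculations.

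The data are already planned. The adverse-event file in SAP Appendix 2 (Table 8) carries a subject number for each event, and the skin-reaction log is kept by patient and visit. The cost is slightly more tabulation, a short SAP amendment and a reworded protocol paragraph, and the stated figure becomes less favourable. No extra patients, visits or samples are needed.
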